10.1 Sample size calculation

The primary goal of this study is to assess high-precision RT with 5x5 Gy in 1 week with respect to 6-month LPFS and to demonstrate that this rate is superior to conventional RT with 5x4 Gy with respect to LPFS of MSCC (hypothesis).

With respect to tumor cell kill, the equivalent dose in 2 Gy fractions (EQD2) of 5x5 Gy is similar to the EQD2 of 10x3 Gy (31.3 Gy vs. 32.5 Gy) and higher than the EQD2 of 5x4 Gy (23.3 Gy) . In a previous prospective non-randomized study, the 6-month LPFS rates were 86% after longer-course RT and 67% after short-course RT, respectively ($p=0.034$). In that study, 95 of 117 patients (81%) in the longer-course RT group had received 10x3 Gy, and 91 of 114 patients (80%) in the short-course RT group had received 5x4 Gy. Thus, assuming - for the present study – that conventional RT with 5x4 Gy in fact results in a 6-month LPFS rate of 67%, an increase by roughly 20 percentage point is considered to be clinically minimal relevant and even appears to be realistic when applying high-precision RT with 5x5 Gy.

The sample size is chosen to firstly obtain prospective phase 2 data that can be interpreted on its own and to secondly allow for comparison with historical data:

- A sample size of at least 40 eligible patients is needed to estimate the probability of LPFS at 6 month with adequate precision, based on the following assumptions:
 - 6-month LPFS can be assumed to be 87%
 - 6-month LPFS is to be estimated with a precision of plus/minus 20 percentage points expressed as the half length of the associated two-sided confidence interval with a confidence coefficient of 95%.
 - The power -i.e. the probability to obtain this precision, should be at least 80%
 - Clopper-Pearson confidence limits are used as the approach for sample size.

Assuming that roughly 10% of enrolled patients will not be eligible for efficacy analysis due to early lost-to-follow-up or due to premature discontinuation of high-precision RT, a total of 44 patients should be enrolled in the prospective part of the trial.

- As described in section 8, the confirmatory study aim is to compare the prospectively collected phase II data with a historical, propensity-score matched cohort collected up to the time of data analysis. Assuming for simplicity and conservative power calculation that this comparison could be conducted with a simple Pearson-Chi-Square test using a two-sided significance level of 5% (10%), a power of 79% (86%) is reached, if 40 patients are treated with high-precision RT and roughly 400 patients of the historical control group qualify for Propensity-Score adjusted comparison and assuming that the expected 6-month LPFS are 87% and 67%, respectively. Taking into account that the more sophisticated propensity-score adjusted statistical analysis (see section 8) will increase statistical power, the power for treatment arm comparison reached

PRE-MODE

with 40 eligible patients in the prospective phase 2 part of the study can be assumed to be at least 80%.

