Inclusion criteria	
 1. Motor deficits of the lower extremities resulting from MSCC, which have persisted for no longer than 30 days 2. Confirmation of diagnosis by magnetic resonance (MR) imaging (computed tomography (CT) allowed) 3. Age 18 years or older 4. Written informed consent 5. Capacity of the patient to contract
Exclusion criteria	
 1. Previous RT or surgery of the spinal areas affected MSCC 2. Symptomatic brain tumor or symptomatic brain metastases 3. Metastases of the cervical spine only 4. Other severe neurological disorders 5. Pregnancy, lactation period 6. Indication for decompressive surgery of affected spinal areas
Statistics/Sample size calculation	
The primary endpoint of this phase 2 study is to assess high-precision RT with 5x5 Gy in 1 week with respect to 6-month LPFS and to demonstrate that this rate is superior to conventional RT with 5x4 Gy (hypothesis).
 
To ensure with 80% power that – in the phase 2 study- the 95% confidence interval for the true 6-month LPFS rate has a precision of +/-20% a total of 44 patients should be enrolled. For comparison of the prospective study results with historical controls, a propensity score approach will be applied to account for baseline differences between treatment arms to balance covariates and remove bias that may arise due to these confounders. Ten relevant prognostic factors will be included. Assuming that roughly 400 historical controls qualify for this comparison, a power of at least 80% will be ensured assuming that the true 6-month LPFS rate with conventional RT with 5x4 Gy is roughly 67% and a 20% percentage increase is considered as clinically relevant.

End of study	The study is completed when all patients have either died or been followed for at least 6 months and analyses, reporting and publication have been finished, or when the study has been terminated due to other reasons (for example patient safety).

PRE-MODE

Flow Chart

	Prior to RT	End of RT	Follow up at 1 month (+/- 2 weeks) following RT	Follow up at 3 months (+/- 2 weeks) following RT	Follow up at 6 months (+/- 2 weeks) following RT
Informed Consent	X				
Medical History/Concomitant Diseases	X				
Prognostic factors	X				
Physical examination	X	X	X	X	X
Inclusion/Exclusion Criteria	X				
Motor Function	X	X	X	X	X
Sensory Function	X	X	X	X	X
Sphincter Dysfunction	X	X	X	X	X
Ambulatory Status	X	X	X	X	X
Pain	X	X	X	X	X

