	
Um mit einer statistischen Power von 80% zu gewährleisten, dass in dieser Phase 2 Studie das 95%-Konfidenzintervall für die wahre LPFS-Rate nach 6 Monaten eine Genauigkeit von +/-20% aufweist, müssen 44 Patienten/innen eingeschlossen werden. Für den Vergleich mit der historischen Kontrollgruppe wird ein Propensity Score Matching durchgeführt, um Unterschiede zwischen beiden Gruppen hinsichtlich Patientencharakteristika und Kovariablen auszugleichen und eine durch mögliche Unterschiede resultierende Verzerrung (Bias) zu vermeiden. Zehn relevante Prognosefaktoren werden hierbei berücksichtigt. Unter der Annahme, dass sich ungefähr 400 Patienten/innen für die historische Kontrollgruppe qualifizieren, wird eine statistische Power von 80% erreicht, wobei davon ausgegangen wird, dass die wahre LPFS-Rate 6 Monate nach konventioneller Strahlentherapie mit 5x4 Gy 67% beträgt und eine Verbesserung von absolut 20% als klinisch relevant angesehen wird.

Ende der Studie	
Die Studie ist abgeschlossen, wenn alle Patienten entweder verstorben sind oder für wenigstens 6 Monate nachbeobachtet wurden und Analysen, Berichte und die Publikation abgeschlossen sind oder die Studie aus anderen Gründen beendet wurde (zum Beispiel Patientensicherheit).

Ablaufplan

	Vor Strahlentherapie	Am Ende der Strahlentherapie	1 Monat (+/- 2 Wochen) nach Strahlentherapie	3 Monate (+/- 2 Wochen) nach Strahlentherapie	6 Monate (+/- 2 Wochen) nach Strahlentherapie
Einverständniserklärung	X				
Anamnese/Begleiterkrankungen	X				
Prognosefaktoren	X				
Ärztliche Untersuchung	X	X	X	X	X
Ein-/Ausschlusskriterien	X				
Motorische Funktion	X	X	X	X	X
Sensibilität	X	X	X	X	X
Blasen-Mastdarm-Störungen	X	X	X	X	X
Gehfähigkeit	X	X	X	X	X
Schmerz	X	X	X	X	X
Distress (Lebensqualität)	X	X	X	X	X
Toxizität*	X	X	X	X	X
LPFS		X*	X	X	X
Gesamt Überleben		X*	X	X	X

*ebenfalls während der Strahlentherapie

2 List of Abbreviations

AE	adverse event
ASIA	American Spinal Injury Association
GCP	good clinical practice
CR	complete response
CRF	case report form
CT	computed tomography
CTCAE	Common Terminology Criteria for Adverse Events
DEGRO	German Society for Radiation Oncology
ECOG	Eastern Cooperative Oncology Group
EQD2	equivalent dose in 2 Gy fractions
LPFS	local progression-free survival
MR	magnetic resonance
MSCC	metastatic spinal cord compression
OS	overall survival
PR	partial response
PTV	planning target volume
QUANTEC	Quantitative Analyses of Normal Tissue Effects in the Clinic
RT	radiotherapy

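### The stated precision criterion (±20 points, 80% probability, true rate 87%) is met from 17 patients, not 40; 40 patients give about ±13 points

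*Combined protocol and SAP*

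**What the plan says.** Section 10.1 gives two purposes for the sample size. The first is precision in the single arm: "The sample size is chosen to firstly obtain prospective phase 2 data that can be interpreted on its own". The second is the comparison with historical controls.

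For the first purpose it states: "A sample size of at least 40 eligible patients is needed to estimate the probability of LPFS at 6 month with adequate precision". The listed assumptions are:

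- a true 6-month LPFS of 87%;
- "6-month LPFS is to be estimated with a precision of plus/minus 20 percentage points expressed as the half length" of the two-sided 95% confidence interval;
- at least 80% probability of obtaining that precision, which the plan calls power;
- Clopper-Pearson limits.

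About 10% is then added for patients not evaluable for efficacy, which gives 44 enrolled.

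The English synopsis condenses this to "the 95% confidence interval for the true 6-month LPFS rate has a precision of +/-20% a total of 44 patients should be enrolled", with 80% power. The German synopsis says the same: "das 95%-Konfidenzintervall für die wahre LPFS-Rate nach 6 Monaten eine Genauigkeit von +/-20% aufweist, müssen 44 Patienten/innen eingeschlossen werden".

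**The concern.** A half length of 20 points is a loose target for a proportion near 87%, and 40 patients is a lot for it. If the stated inputs do not give 40, the first of the two reasons for the sample size cannot be reproduced, and the text understates the precision the trial will deliver.

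The meaning of the criterion is also at stake. A half-length target only describes how wide the interval will be. A lower-limit target of 67% would mean that the single-arm result alone excludes rates below the 67% assumed for 5x4 Gy. The plan wants the phase 2 data to be interpretable on their own, so readers need to know which of the two was meant.

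**Working it through.** **Inputs (all from section 10.1).** True rate p = 0.87; two-sided 95% Clopper-Pearson interval; half length at most 0.20; probability at least 0.80; stated result n = 40.

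**Method.** For x patients free of local progression out of n, the limits are L = Beta⁻¹(0.025; x, n−x+1) and U = Beta⁻¹(0.975; x+1, n−x), with U = 1 when x = n. The half length is (U−L)/2. The probability of meeting the criterion is the sum of Binomial(n, 0.87) probabilities over every x for which it holds.

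**Step 1: the criterion as written.**

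- n = 16: x = 13 gives 0.544 to 0.960, half length 0.208 (fails); x = 14 gives 0.617 to 0.984, half length 0.184 (passes). P(X ≥ 14) = 0.654.
- n = 17: x = 13 gives half length 0.215 (fails); x = 14 gives 0.566 to 0.962, half length 0.198 (passes). P(X ≥ 14) = 0.829.
- n = 18: 0.801. n = 20: 0.892. The probability stays at or above 0.80 at every n from 17 to 120, the largest size checked.
- From n = 27 the criterion holds for every possible outcome.
- n = 40: the largest half length over all outcomes is 0.162, so the probability is 1.00.

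The plan's 40 is not reproduced; the stated inputs give 17.

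**Step 2: what 40 patients deliver at a true rate of 87%.**

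| x of 40 | 95% interval | Half length | P(X ≥ x) |
|---|---|---|---|
| 32 | 0.644 to 0.910 (rounded up from 0.9095) | 0.133 | 0.932 |
| 33 | 0.672 to 0.927 | 0.127 | 0.859 |

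The half length is therefore at most about 12.7 points with probability 0.859, and its expected value is 11.2 points. If all 44 enrolled patients are evaluable, x = 36 gives half length 0.123, with P(X ≥ 36) = 0.890.

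**Step 3: other readings of the width.**

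| Reading | Smallest n | Probability there | Probability at n − 1 |
|---|---|---|---|
| Half length ≤ 0.20 (as written) | 17 | 0.829 | 0.654 |
| Farther limit within 0.20 of the estimate | 27 | 0.871 | 0.757 |
| Full width ≤ 0.20 | 61 | 0.837 | 0.752 |

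None gives 40. The drop-out allowance does not explain the gap either, because it is applied after 40 (40 × 1.1 = 44).

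**Step 4: a criterion that does fit.** Take a lower 95% limit of at least 0.87 − 0.20 = 0.67, with probability at least 0.80:

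| n | 35 | 36 | 37 | 38 | 39 | 40 | 41 | 42 | 43 | 44 |
|---|---|---|---|---|---|---|---|---|---|---|
| Probability | 0.700 | 0.820 | 0.802 | 0.782 | 0.762 | 0.859 | 0.844 | 0.828 | 0.811 | 0.890 |

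The probability first passes 0.80 at n = 36, falls below it at 38 and 39, and stays at or above it at every n from 40 to 120. At n = 40 the criterion requires at least 33 patients free of local progression, since 32 of 40 has a lower limit of 64.4%.

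**The case against.** The strongest reply is that nothing is at risk. Forty patients satisfy the stated ±20 points with certainty, so only the claim that 40 are needed fails. The number also has a second, separate basis: section 10.1 calls the historical comparison the confirmatory aim and gives 79% power for 40 against about 400 at a two-sided 5% level. A normal-approximation check gives 80.2%, close to that figure. All of this stands. It means the trial is not shown to be the wrong size, but it does not repair the precision argument, which the plan puts first.

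A second reply is that the synopses never mention half length, Clopper-Pearson or 87%, so their ±20% could loosely mean limits within 20 points of the assumed true rate, which is the reading that fits 40. That is fair for the synopses taken alone. Section 10.1, however, defines the precision explicitly as a half length, and the synopses summarise that section.

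A third reply is that the plan attaches no decision rule to the single-arm interval, so 33 of 40 has no formal role. That is correct. The figure only shows what the lower-limit criterion would imply. That this criterion was the real basis is an inference: it gives 40 only if the probability must stay above 0.80 for all larger n, and the documents cannot confirm it.

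**Conclusion.** The concern holds. With the inputs in section 10.1 the criterion is met from n = 17, against 40 stated, and no reading of the stated width gives 40. At 40 patients the precision is about ±13 points (half length at most 12.7 points with probability 0.859), not ±20. The calculation is exact and rests only on the plan's assumed rate of 87%, its interval method and its 80% requirement.

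The error lies in the description of the justification. It is not evidence that the sample size should change. It should be corrected because it concerns the first stated reason for the sample size and appears in three places.

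**What to change.** The sponsor should first confirm from the original calculation which criterion produced 40. Then section 10.1 and both synopses should be reworded to match.

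- **If the lower limit was the basis:** replace the half-length criterion with: *The lower limit of the two-sided 95% Clopper-Pearson interval is at least 67% with at least 80% probability (0.86 with 40 evaluable patients and a true 6-month LPFS of 87%).*
- **Otherwise:** state what 40 patients deliver: *With 40 evaluable patients and a true 6-month LPFS of 87%, the half length of the two-sided 95% Clopper-Pearson interval is at most about 13 percentage points with at least 80% probability (12.7 points, probability 0.86).* This sentence describes the precision obtained. It should not be presented as the original derivation of 40.

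The cost is wording in three places. Sample size, analysis and conduct do not change.

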10.2. Statistical analyses

10.2.1 Primary endpoint:

The primary endpoint (LPFS of MSCC) will be evaluated based on the sample size calculations described above. The evaluation will be performed in those patients, who are available for assessment of the primary endpoint and have received at least 80% of the planned RT dose. Due to the open nature of the study, a blind data review is not necessary. The safety population includes all patients who have received at least 1 fraction of high-precision RT.

LPFS is defined as freedom from progression of motor deficits during RT and freedom from an in-field recurrence of MSCC (i.e. freedom from motor deficits due to a recurrence of MSCC in the previously irradiated parts of the spine) following RT [5]. Deterioration of motor deficits during RT will be counted as LPFS of 0 months. Freedom from an in-field recurrence following RT will be referenced from the last day of RT. To investigate clinically important, sustainable effects of precision radiotherapy and avoid over-evaluation of early temporal shifts without any longer term relevance, study design and analysis focuses on binary endpoints evaluated at 6-months rather than time-to-event analyses.

10.2.2 Secondary endpoints:

Secondary endpoints:

An improvement or deterioration of the motor function will be defined as a change of at least 1 point on a 5-point scale [17]. Effect of RT on motor function and post-RT ambulatory rates will be evaluated directly after RT and at 1, 3 and 6 months following RT in those patients who are alive and available for assessment. To investigate whether propensity scores removed bias due to differences in covariates between studies and to compare binary study endpoints after stratification of patients by propensity scores Cochran-Mantel-Haenszel tests were performed. P-values of <0.05 are considered significant.

Overall survival (OS) will be counted from the last day of RT. To investigate clinically important, sustainable effects of precision radiotherapy and avoid over-evaluation of early temporal shifts without any longer term relevance, study design and analysis focuses on binary endpoints evaluated at 6-months rather than time-to-event analyses. The analysis of OS will be conducted in the intent-to-treat population.

Data regarding sensory deficits, sphincter dysfunction, pain, distress and toxicity will only be assessed in the phase 2 study.

11 Ethical and Legal Principles

The examinations to be carried out as part of this study are all considered standard procedures. There are no additional laboratory tests, X-rays or other examinations that could be potentially burdensome for the patient.

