8.3.7 Toxicity

Toxicity will be assessed according to CTCAE 4.03 during RT, directly after RT and at 1, 3 and 6 months following RT [20]. If radiation myelopathy is suspected (i.e. deterioration according to the modified ASIA scale [19]), spinal MR-imaging will be performed.

9 Comparisons to Historical Control Group

The patients of this study who received high-precision RT with 5x5 Gy for MSCC will be matched to historical control group treated with 5x4 Gy of conventional RT between 2001 and 2016. This data set consists of 680 patients.

The patients of the control group are part of an already existing anonymized database. To be eligible for control group, patients fulfilling the same inclusion criteria and exclusion criteria as defined in the prospective phase II study are considered. Furthermore, to be consistent with efficacy analysis of phase II study, patients of the historical control group must have received at least 80% of the planned RT dose. This will lead to more than 600 patients qualifying for the comparison with the prospectively collected phase 2 data.

For comparison purposes, a propensity score approach will be applied to account for baseline differences between treatment arms to balance covariates and remove bias that may arise due to these confounders. A propensity score is a conditional probability of assignment to a particular treatment given a number of baseline covariates. Except for unmeasured potential confounding factors, patients having the same propensity score but assigned to different treatments will tend to have the same (or nearly the same) distributions on their background covariates and thus are considered to be similar to random assignment of treatments. To estimate the odds of receiving a specific radiotherapy a non-parsimonious multivariable logistic regression model will be estimated. Covariates to be included in the model will be the following ten prognostic factors [16]:

- Age (2 groups, depending on median age)
- Gender
- Type of primary tumor (breast cancer vs. prostate cancer vs. myeloma/lymphoma vs. lung cancer vs. other tumors)
- Interval from tumor diagnosis to MSCC (≤ 15 vs. > 15 months)
- Number of involved vertebrae (1-2 vs. ≥ 3)
- Other bone metastases at the time of RT (no vs. yes)
- Visceral metastases at the time of RT (no vs. yes)
- Time developing motor deficits prior to RT (1-7 days vs. 8-14 days vs. > 14 days)
- Ambulatory status prior to RT (no vs. yes)

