- Eastern Cooperative Oncology Group (ECOG) performance score (1-2 vs. 3-4)

Once estimated, adjustment will be accomplished by stratifying the data set on the propensity score, calculating the treatment effect within strata and then pooling the strata-specific treatment effect estimates.

Rosenbaum and Rubin have shown that perfect stratification based on the propensity score will produce strata where the average treatment effect within strata is an unbiased estimate of the true treatment effect [21]. Due to the differences in total sample size between the phase II study and the historical data set, the stratum boundaries will be based on the values of the propensity score for the phase II data alone.

One approach is to use quintiles of the estimated propensity scores to determine the cut-offs for the different strata. The success of propensity score approach will be examined by examining the covariate imbalance between treatment arms before and after adjusting for their propensity quintile. This will be done using a two-way analysis of variance model which includes main effects for propensity score quintile (codes as a class variable with 4 degrees of freedom) and treatment arm. The F-statistic for treatment arm after adjustment for propensity score quintiles will then be compared with the F-statistics for treatment arm prior to adjustment for propensity score quintile to determine whether balance was achieved after stratification based on the propensity score.

PRE-MODE

Furthermore, the propensity score will be evaluated for good calibration as measured by the propensity score predicted and observed proportions of treatment group arms within quintiles of the propensity score. To investigate whether propensity scores removed bias due to differences in covariates between studies and to compare binary study endpoints after stratification of patients by propensity scores Cochran-Mantel-Haenszel tests were performed.

Comparisons between the patients of the phase 2 study and the historical control group will be performed for LPFS, OS, motor function and ambulatory status.

10 Statistics

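### Ambulatory status and motor change are compared with the historical controls over propensity strata alone; using baseline function as well would recover power and close a route for bias

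*Combined protocol and SAP*

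**What the plan says.** Section 9 states that comparisons with the controls "will be performed for LPFS, OS, motor function and ambulatory status". The method is that "adjustment will be accomplished by stratifying the data set on the propensity score", with stratum-specific effects then pooled. Quintiles are offered as a possible choice ("One approach is to use quintiles of the estimated propensity scores to determine the cut-offs for the different strata"), and "the stratum boundaries will be based on the values of the propensity score for the phase II data alone". Section 10.2.2 repeats the test for binary endpoints: "to compare binary study endpoints after stratification of patients by propensity scores Cochran-Mantel-Haenszel tests were performed".

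Baseline function enters the propensity model as ambulatory yes/no, with ECOG 1-2 vs 3-4 as a partial proxy. The five-level Tomita grade (0-4) is recorded before RT (sections 8.2 and 8.3.2), but it is neither a propensity term nor a stratum. Section 10.2.2 nevertheless defines the motor endpoint as a change from that grade: "An improvement or deterioration of the motor function will be defined as a change of at least 1 point on a 5-point scale". Both endpoints are assessed "in those patients who are alive and available for assessment". No outcome model with baseline function is planned.

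**The concern.** There are two separate issues.

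**Ambulatory status.** An estimated propensity score that contains baseline ambulation makes the two groups nearly equal on it within strata. Chance imbalance in baseline ambulation then adds little to the variation of the comparison. The CMH variance is still computed as if that variation were present. If baseline ambulation predicts later ambulation, the test is too conservative and loses power, in a phase 2 group of about 40 or fewer.

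**Motor change.** Grades 3 and 4 are both non-ambulatory and so look the same to the propensity model, as do grades 1 and 2. Yet the chance of a one-point change can depend on the starting grade, in part by construction: grade 4 is the worst score and cannot worsen, while grade 3 can. The groups could therefore be balanced on ambulatory status, differ in grade mix, and show a difference that is not a treatment effect. The balance checks in section 9 are described for the covariates, and grade is not among them.

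**Working it through.** **1. The plan's own power figure.** The documents give none for these endpoints. The only comparative figure, in section 10.1, is for LPFS: 79% at two-sided 5% (86% at 10%) for 87% vs 67%, 40 vs 400. The pooled formula gives:
- p = (40×0.87 + 400×0.67)/440 = 0.688
- SE0 = √[0.688×0.312×(1/40 + 1/400)] = 0.0768
- SE1 = √[0.87×0.13/40 + 0.67×0.33/400] = 0.0581
- power = Φ[(0.20 − 1.96×0.0768)/0.0581] = 80.2%, close to the stated 79%. The same formula at 10% gives 89.7%, not 86%; that gap has no bearing on this point.

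**2. Inputs.** From the plan: 40 vs 400, ten propensity factors, quintile cut-offs from phase 2 patients, CMH, 5% (taken as two-sided). Assumed, because the documents are silent: post-RT ambulatory rates by baseline grade, covariate distributions, an odds ratio of 3 for power and, for the hand formula, a baseline grade mix (1/2/3/4) of 25/30/33/12%, which makes w = 55% ambulatory.

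**3. Ambulatory endpoint, by hand.** Let a and b be the post-RT ambulatory rates of patients who were and were not ambulatory at baseline, and p = wa + (1−w)b. With baseline exactly balanced, the true variance is a fraction 1−R² of what CMH assumes, where R² = w(1−w)(a−b)²/[p(1−p)]. The actual error is 2[1 − Φ(1.96/√(1−R²))].

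Example with a = 95%, b = 30%: p = 0.6575; R² = 0.2475×0.4225/0.2252 = 0.464; √(1−R²) = 0.732; 1.96/0.732 = 2.68; error 0.7%.

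**4. Ambulatory endpoint, simulated** (mostly 3,200 to 8,000 trials per scenario, propensity score estimated each time). Power is for propensity strata alone vs strata plus baseline ambulatory status.

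| Assumed post-RT ambulatory %, grades 1/2/3/4 | Error by hand | Error simulated | Power, alone vs plus baseline | Ratio |
|---|---|---|---|---|
| 98/92/35/8 | 0.6% | 0.7% | 23% vs 49% | 0.47 |
| 95/95/30/30 | 0.7% | 0.9% | 34% vs 57% | 0.60 |
| 95/95/40/40 | 1.4% | 1.7% | 38% vs 55% | 0.69 |
| 90/90/30/30 | 1.3% | 1.7% | 44% vs 63% | 0.70 |
| 95/85/45/20 | 2.0% | 2.1% | 43% vs 57% | 0.75 |
| 85/75/55/40 | 4.0% | 3.8% | 65% vs 67% | 0.97 |
| baseline not prognostic | 5.0% | 4.9% | no loss expected (R² = 0) | about 1 |

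Adding baseline ambulatory status, or grade, as a stratum brings the error to 4.7-5.3%. With fewer assessable patients (24 vs 240 or 30 vs 300), propensity strata alone still give 0.7-0.9% in the first row's scenario and 1.8-2.0% for 95/85/45/20.

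**5. Is the ambulatory comparison confounded?** With a 15-point difference in baseline ambulation and strong dependence, the crude test rejects 25% of the time under no effect. The propensity-stratified test rejects 1.6%. The planned method does remove this confounding.

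**6. Motor improvement under no treatment effect.** Assume improvement rates of 15/50/35/10% for grades 1-4 and w = 55% in both groups. Among ambulatory patients, 50% of controls and 30% of phase 2 patients are grade 1. Among non-ambulatory patients, 70% and 90% are grade 3.
- Controls: 0.55×(0.5×0.15 + 0.5×0.50) + 0.45×(0.7×0.35 + 0.3×0.10) = 30.25%
- Phase 2: 0.55×(0.3×0.15 + 0.7×0.50) + 0.45×(0.9×0.35 + 0.1×0.10) = 36.35%
- Spurious difference 6.1 points; pooled p = 0.308; SE = √[0.308×0.692×0.0275] = 0.0766; shift 0.80 SE; rejection Φ(−1.16) + Φ(−2.76) = about 12.5%

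The simulation gives 12.4% with propensity strata, 12.4% with ambulatory status added and 4.4% with grade added. Over the simulated mixes that differ by 10 to 20 points and two sets of grade-dependent rates, the planned test rejects 5.7-12.4% and the grade-stratified test 4.4-4.9%. With equal mixes, or with improvement independent of grade, the planned test stays at 4.8-4.9%. Deterioration was not simulated.

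**The case against.** The strongest objection is that none of these sizes is a property of the plan. A reader might infer from one strong scenario that the ambulatory test runs at about 1.6% error with little over half the attainable power. The documents do not support that: they give no transition rates and no effect size for this endpoint, they list ambulatory status as one of ten factors without ranking it, and the error ranges from 0.7% to nearly 5% with the assumption made. This stands, and only the range can be reported.

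A reader might also infer that the ambulatory result is biased, or that it needs the full grade. Neither follows. Baseline ambulation is already in the propensity model, and ambulatory yes/no as a stratum restores the level as well as grade does.

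Nor do these comparisons carry a claim that motor outcome is no worse than after 5x4 Gy. Section 10.1 names one confirmatory comparison and powers it on LPFS; the motor and ambulatory comparisons are secondary.

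The motor-change bias needs both a mix difference and grade-dependent change, and the documents establish no mix difference. That stands too, but nothing planned would detect or correct one against controls treated from 2001 to 2016.

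Finally, quintiles are only one option, and section 9 expects more than 600 controls rather than 400. Neither changes the mechanism.

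**Conclusion.** The point holds as an inexpensive improvement to two secondary comparisons. For ambulatory status, the planned test is valid but possibly inefficient: error between about 0.7% and 5%, and power about 0.5 to 1.0 times what is attainable, with a large loss only if baseline function strongly predicts outcome. For motor change there is a conditional route to bias: about 6% to 12% null rejection instead of 5%, if grade mix differs by 10 to 20 points within ambulatory class and improvement depends on grade. All these figures rest on assumed rates and covariate distributions. The primary LPFS comparison is not affected by this point.

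**What to change.** In sections 9 and 10.2.2, keep the binary endpoints and add:
- **Ambulatory status:** CMH stratified by propensity stratum and baseline ambulatory status, or a logistic model with treatment group, propensity stratum and baseline ambulatory status.
- **Motor improvement and deterioration:** the same, with baseline Tomita grade in place of ambulatory status.

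State in advance which form is used, and use the regression form if cells are sparse. An ordinal analysis of the follow-up grade is optional; it would depart from the plan's stated focus on binary endpoints and is not needed to resolve this point.

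**Cost:** a change of wording, with no new data collection in the prospective part. The main drawback is sparse strata: 40 patients over five quintiles is 8 per stratum, and about 2 per cell once split by four grades. The grade must also be available in the historical database. The documents do not say so explicitly, but the planned change score already requires it.
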